### **9.3.2 Study Drug Dose and Duration**

All subjects will receive a TC of VX-445/TEZ/IVA at the same dosage as that in the VX-445 Phase 3 pivotal trials.

The overall treatment duration will be up to 96 weeks, which is considered sufficient for the evaluation of long-term safety.

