## 9.9 Removal of Subjects

Subjects may withdraw from the study at any time at their own request. Subjects may be withdrawn from study drug treatment at any time at the discretion of the investigator or Vertex for safety, behavior, noncompliance with study procedures, or administrative reasons.

In addition, a subject must be discontinued from study drug treatment if the subject meets any of the following criteria:

- Meets any of the stopping (discontinuation) criteria (Section 9.8)
- Becomes pregnant (Section 11.4.9.2)

If a subject does not return for a scheduled visit, reasonable effort will be made to contact the subject. In any circumstance, reasonable effort will be made to document subject outcome. The investigator will inquire about the reason for withdrawal, request that the subject return all unused investigational product(s), request that the subject return for an ETT Visit and Safety Follow-up Visit, if applicable (Section 9.1.2), and follow up with the subject regarding any unresolved AEs.

If the subject withdraws consent or assent for the study, no further assessments will be performed. Vertex may retain and continue using the study data and samples after the study ends, and may use the samples and information in the development of the study compounds, and for other drugs and diagnostics, in publications and presentations, and for education purposes. If the subject withdraws from the study, the study data and samples collected will remain part of the study. A subject will not be able to request the withdrawal of his or her information from the study data. A subject may request destruction of the samples collected from him or her during the study as long as those samples can be identified as his or her samples.

With the exception of subjects who cannot access the commercial product after regulatory approval because reimbursement by the subject's insurance carrier (whether government or private payer) is not yet available or because the subject lacks insurance coverage, subjects who become eligible to receive commercially available VX-445/TEZ/IVA by prescription of a physician may be discontinued from study drug dosing and will complete the ETT Visit before beginning commercially available VX-445/TEZ/IVA dosing. The Safety Follow-up Visit will not be required if the subject immediately continues on commercially available VX-445/TEZ/IVA.

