### 12.1 Sample Size and Power

The primary objective of the study is the evaluation of the long-term safety and tolerability of VX-445/TEZ/IVA. This is an open-label study that will enroll subjects who entered the Treatment Period in Study 659-105 and meet eligibility criteria.

Over 400 subjects are expected to enroll in this open-label study of up to approximately 100 weeks duration. With this number of subjects exposed to VX-445/TEZ/IVA treatment, AEs by Preferred Term (PT) that occur with a frequency of >1% will be ruled out with 95% confidence, when 0 events are observed in that PT.

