## 6.2 Sample Size and Power

The primary objective of the study is the evaluation of the long-term safety and tolerability of ELX/TEZ/IVA. This is an open-label study that enrolled subjects previously enrolled in Study 659-105 and met the Study 445-113 eligibility criteria.

Over 400 subjects were enrolled. With this number of subjects exposed to ELX/TEZ/IVA treatment, AEs by Preferred Term (PT) that occur with a frequency of >1% will be ruled out with 95% confidence, when 0 events are observed in that PT.

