## **7 ANALYSIS SETS**

The following analysis sets are defined: All Subjects Set and Safety Set.

The **All Subjects Set** for Parts A and B are defined as all subjects who were enrolled (defined as subject having data in the clinical database) in Part A or Part B of this study, respectively. This analysis set will be used for individual subject data listings and disposition summary tables unless otherwise specified.

The **Safety Sets** for Part A and B are defined as all subjects who have received at least 1 dose of study drug in Part A or Part B of this study, respectively. The Safety Set will be used for all safety analyses unless otherwise specified.

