- Related serious TEAEs

- TEAEs leading to death

Summaries will be presented separately for Parts A and B by MedDRA SOC and PT using frequency counts and percentages (i.e., number and percentage of subjects with an event) and the exposure adjusted event rate (except for summary by strongest relationship and maximum severity). When summarizing the number and percentages of subjects, subjects with multiple occurrences of the same adverse event or a continuing adverse event will be counted once, and only the maximum severity level will be presented in the severity summaries, and the strongest relationship level in the relationship summaries.

Additional summary tables separately for Parts A and B will be presented for TEAEs showing number, percentage of subjects, and the exposure adjusted event rate

- All TEAEs by PT

All AEs, including pretreatment AEs, TEAEs, and post-treatment AEs, will be presented in an individual subject data listing based on the All Subjects Set separately for Parts A and B. In addition, a listing containing individual subject adverse event data for TEAEs leading to treatment discontinuation, TEAEs leading to treatment interruption, Grade 3/4 TEAEs, SAEs and all deaths will be provided, with a flag indicating the TEAE status for SAEs and deaths for Parts A and B separately.

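### Part A adverse events are pooled over the whole treatment-emergent period, so if many subjects leave early the readable TEAE tables can understate late-onset risk

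*SAP*

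**What the plan says.** Long-term safety and tolerability is the only objective, and Protocol 9.3.2 justifies the duration: "The overall treatment duration will be up to 96 weeks, which is considered sufficient for the evaluation of long-term safety".

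SAP 8.4 bases the Part A safety analyses on the Part A treatment-emergent (TE) Period in the Part A Safety Set. SAP 7 defines the Safety Sets as "all subjects who have received at least 1 dose of study drug in Part A or Part B of this study, respectively". SAP 8.1 runs the Part A TE Period from first dose to 28 days after the last dose, or to completion of participation if that is earlier. Within that single window, SAP 8.4.1 presents TEAEs "by MedDRA SOC and PT using frequency counts and percentages (i.e., number and percentage of subjects with an event) and the exposure adjusted event rate"; the tables by strongest relationship and maximum severity carry no rate.

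Protocol 9.9 provides a way out before Week 96: "subjects who become eligible to receive commercially available VX-445/TEZ/IVA by prescription of a physician may be discontinued from study drug dosing". It excepts subjects who cannot obtain the approved product for want of reimbursement or insurance cover. Protocol 9.10 does not replace leavers.

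On precision, Protocol 12.1 says "Over 400 subjects are expected to enroll in this open-label study of up to approximately 100 weeks duration" and SAP 6.2 reports "Over 400 subjects were enrolled". Both draw the same conclusion, in the SAP's words: "AEs by Preferred Term (PT) that occur with a frequency of >1% will be ruled out with 95% confidence, when 0 events are observed". The zero count refers to the term concerned.

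SAP 8.2.5 already tabulates exposure on a 24-week grid (up to 24, 24 to 48, 48 to 72, 72 to 96 and over 96 weeks in Part A) and gives total patient-weeks and patient-years. The grid is not applied to adverse events.

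**The concern.** The study asks what happens during prolonged treatment. A percentage that divides all events in the TE Period by everyone ever dosed is a fair 96-week figure only if most subjects are followed for about 96 weeks. If a sizeable group leaves earlier, its members stay in the denominator for events they could no longer show. An event that tends to start late then looks rarer than it is among those still on treatment.

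The exposure-adjusted rate is the natural remedy, but a single rate over the whole period assumes a constant hazard. If the hazard rises with time on drug, the rate averages a low early hazard with a high late one, and early leavers shift the weight towards the early part.

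No readable TEAE summary table gives incidence by time since first dose. Laboratory values, ECGs, vital signs, oximetry and spirometry are all summarised by visit, so the gap is specific to adverse events. At stake is whether the summary tables can show a late-emerging event at its true frequency among those at risk.

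**Working it through.** **Inputs from the documents.** n = 400, the lower bound of the stated over 400 subjects (Protocol 12.1, SAP 6.2). Threshold 1%, confidence 95%, 0 events (SAP 6.2). The documents do not say whether the 95% is one- or two-sided, so both are shown. Treatment lasts up to 96 weeks (Protocol 9.3.2). Retention is not given, so a range is assumed.

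**Step 1: reproduce the plan's own figure.** With 0 events in n subjects the exact upper bound is 1 − α^(1/n).

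- One-sided, α = 0.05: 1 − 0.05^(1/400) = 0.746%.
- Two-sided, α = 0.025: 1 − 0.025^(1/400) = 0.918%.
- Chance of at least one event if the true frequency is 1%: 1 − 0.99^400 = 98.2%.

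Both bounds lie below 1%. The statement is right for subjects with at least one dose.

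**Step 2: how many subjects must be observed for a 1% bound.** Smallest n = ln(α)/ln(0.99), rounded up.

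- One-sided: ln(0.05)/ln(0.99) = 298.07, so 299 subjects, or 299/400 = 74.75%.
- Two-sided: ln(0.025)/ln(0.99) = 367.04, so 368 subjects, or 368/400 = 92%.

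**Step 3: zero-event bound for a late interval, by assumed retention of 400.**

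| Still observed | Upper bound, one-sided | Upper bound, two-sided |
|---|---|---|
| 400 (100%) | 0.75% | 0.92% |
| 360 (90%) | 0.83% | 1.02% |
| 320 (80%) | 0.93% | 1.15% |
| 300 (75%) | 0.99% | 1.22% |
| 280 (70%) | 1.06% | 1.31% |
| 200 (50%) | 1.49% | 1.83% |
| 80 (20%) | 3.68% | 4.51% |

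**Step 4: does the pooled rate remove the dilution?** All inputs to this illustration are assumed: 400 subjects, no events before Week 48, 2 per 100 patient-years afterwards, all leavers going at Week 48, and at most one event per subject. The 28-day tail is ignored.

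- Patient-years to Week 48: 400 × 48/52 = 369.23.
- Patient-years after Week 48, with a fraction r staying to Week 96: 369.23 × r.
- Expected events: 0.02 × 369.23 × r.
- Pooled rate: events divided by all patient-years. Crude percentage: events/400.

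| Staying to Week 96 | Expected events | Pooled rate per 100 patient-years | Crude % | Rate after Week 48 |
|---|---|---|---|---|
| 100% | 7.38 | 1.00 | 1.85% | 2 |
| 50% | 3.69 | 0.67 | 0.92% | 2 |
| 25% | 1.85 | 0.40 | 0.46% | 2 |

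For r = 50%: 3.69/(369.23 + 184.62) = 0.67 per 100 patient-years, and 3.69/400 = 0.92%. The risk to a subject on treatment after Week 48 is the same in every row; both reported summaries fall as retention falls. Even with full retention the pooled rate is half the late rate, because it averages over 48 event-free weeks.

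**The case against.** Several points on the other side stand.

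*Not all of the SAP can be read.* Its numbering passes from 8.4.8 to 8.6. Appendix E lists terms for events of special interest, yet the readable 8.4.1 describes no analysis of them. At least one adverse event analysis is therefore out of view, and one by time of onset cannot be excluded. The point is limited to the readable text.

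*Timing is not lost.* A reader might infer that the report could not tell an event after a year from one in the first weeks. The documents do not support that. Protocol 13.1.1.3 collects the date of first occurrence, and SAP 8.4.1 lists all adverse events by subject. Part B has its own TE Period and tables. What the readable plan lacks is a summary with a denominator for each interval. Listings supply none, and exposure categories and disposition show who left but not when events began.

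*The 1% statement is not an error.* A reader might infer that it fails for long-term treatment. It is a precision statement about subjects exposed, conditional on zero events in a term; it claims no duration, and it reproduces. Whether it carries over to late exposure depends on a retention figure the documents do not give. Nor would a term with early events and none later be declared ruled out, because the zero-event condition would not be met.

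*Exit is conditional.* A reader might also infer that subjects can move to commercial drug at any time. Protocol 9.9 requires eligibility for an available product, is permissive, and has the access exception. SAP 6.1 names Australia, Canada, Spain and Poland as lacking commercial supply.

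*Interval tables will be sparse* in an uncontrolled, descriptive study. That is true for rare terms, and is a reason to keep the set small.

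**Conclusion.** The point holds as a limited gap that is cheap to close. In the readable SAP, Part A TEAE tables give one cumulative percentage on all dosed subjects and, for most tables, one pooled rate. If many subjects leave early, the percentage understates late-onset risk, and the rate repairs this only under a constant hazard. In the illustration, a late rate of 2 per 100 patient-years appears as 1.00 with full retention and 0.40 with 25% retained. Those sizes rest on assumed retention, exit time and hazard, and the actual loss may be small.

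The 1% statement is correct for subjects with at least one dose and needs only clarification. As evidence on a late interval it reaches 1% only with at least 299 subjects observed (one-sided 95%) or 368 (two-sided 95%).

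The conclusion would change if the unreadable SAP section already provides TEAE incidence by time since first dose.

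**What to change.** In SAP 8.4.1, add Part A TEAE tables for all TEAEs, serious TEAEs and TEAEs leading to discontinuation, by onset interval on the 24-week grid of SAP 8.2.5. Use subjects still in the TE Period at the start of each interval as denominator for percentages, and patient-time within the interval for rates. Show both denominators in the table.

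As a clarification in SAP 6.2 and Protocol 12.1, say that the 1% statement refers to subjects with at least one dose. Where it is read as evidence on long exposure, report the zero-event upper bound for the number actually reaching each interval, and state whether the 95% is one- or two-sided.

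The cost is SAP wording and a few tables from data already collected, with no new visits or tests. The downsides are sparse cells for rare terms and, if many subjects have left, late-interval bounds above 1%.

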#### **8.4.2 Clinical Laboratory Assessments**

Summaries of laboratory values will be provided separately for Parts A and B based on the Safety Set.

For the treatment-emergent laboratory assessments, the observed values and change from baseline values of the continuous hematology, coagulation and chemistry results will be summarized in SI units at each visit during the TE period of the corresponding part separately for Parts A and B.

The number and percentage of subjects with selected test values meeting at least 1 threshold analysis criterion event during the TE period of the corresponding part will be summarized separately for Parts A and B. The threshold analysis criterion shift from baseline will also be summarized for selected laboratory test values separately for Parts A and B. The threshold analysis criteria are provided in [Appendix D](#).

For selected LFT laboratory test (alanine transaminase [ALT], aspartate transaminase [AST], alkaline phosphatase [ALP], and total bilirubin), a scatter plot of the maximum treatment-emergent value versus the baseline value corresponding to  $\times$ ULN (upper limit of normal) will be presented for the each part. Furthermore, a scatter plot of the maximum treatment-emergent value of ALT and AST, separately, versus the maximum treatment-emergent value of total bilirubin corresponding to  $\times$ ULN will also be presented for the each part.

Results of positive urine/serum pregnancy test will be listed in individual subject data listings only separately for Parts A and B. For positive serum pregnancy listing, subjects with serum HCG which are abnormally high will be selected separately for Parts A and B.

In addition, a listing containing individual subject hematology, chemistry, coagulation and urinalysis values will be provided separately for Parts A and B. This listing will include data from both scheduled and unscheduled visits.

### **8.4.3 Electrocardiogram**

Summaries of ECG values will be provided separately for Parts A and B based on the Safety Set.

For the following ECG interval measurements during the TE period of the corresponding part, a summary of observed values and change from baseline values (in msec) will be provided at each visit separately for Parts A and B: RR interval, PR interval, QT interval, and QT corrected for HR (QTcF), QRS duration, and HR (beats per minute).

The number and percentage of subjects meeting at least 1 threshold analysis criterion during the TE period of the corresponding part will be summarized separately for Parts A and B. The threshold analysis criteria are provided in [Appendix D](#).

In addition, a listing containing individual subject ECG values will be provided separately for Parts A and B. This listing will include data from both scheduled and unscheduled visits.

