### **12.3.3.3 Electrocardiogram**

For the treatment-emergent ECG measurements, a summary of observed values and change from baseline values will be provided at each time point during the TE Period in this study, for the following standard 12-lead ECG interval measurements (in msec): RR, PR, QT, QTc for heart rate (HR) interval (QTcF), QRS duration, and HR (beats per minute [bpm]).

The number and percentage of subjects with at least 1 threshold analysis event during the TE Period in this study will be summarized. The threshold analysis criteria will be provided in the SAP.

Additional ECG analyses may be described in the SAP.

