### **8.4.4 Vital Signs**

Summaries of vital sign values will be provided separately for Parts A and B based on the Safety Set.

For the vital sign measurements during the TE period for the Safety Set for the corresponding part, the observed values and change from baseline values will be summarized at each visit separately for Parts A and B. The following vital signs parameters will be summarized: BMI ( $\text{kg}/\text{m}^2$ ), weight (kg), systolic and diastolic blood pressure (mm Hg), body temperature ( $^{\circ}\text{C}$ ), pulse rate (beats per minute), and respiratory rate (breaths per minute).

The number and percentage of subjects meeting at least 1 threshold analysis criterion during the TE period for the corresponding part will be summarized separately for Parts A and B. The threshold analysis criteria are provided in [Appendix D](#).

In addition, a listing containing individual subject vital sign values will be provided separately for Parts A and B. This listing will include data from both scheduled and unscheduled visits.

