### **8.4.5 Pulse Oximetry**

Summaries of pulse oximetry values will be provided separately for Parts A and B based on the Safety Set.

For the percent of oxygen saturation measurements using pulse oximetry during the TE period for the Safety Set for the corresponding part, a summary of observed values and change from baseline values will be provided at each visit separately for Parts A and B.

The number and percentage of subjects with shift changes from baseline (normal/missing and low according to the reference range) to the lowest percent of oxygen saturation during the TE Period for the corresponding part will be summarized separately for Parts A and B. The reference range for normal oxygen saturation is specified as  $>95\%$ , and  $\leq 95\%$  for low oxygen saturation.

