**Table 11-5 Threshold Analysis Criteria for ECGs**

Parameter	Threshold Analysis	Comments
	Tachycardia	Per HV grade 1, 2, 3, plus shift change
	>100 bpm >115 bpm >130 bpm Increase from baseline $\geq 10$ bpm Increase from baseline $\geq 20$ bpm >100 bpm and increase from baseline $\geq 10$ bpm >100 bpm and increase from baseline $\geq 20$ bpm	
PR	$\geq 240$ ms $\geq 300$ ms $\geq 200$ ms and increase from baseline $\geq 40$ ms $\geq 200$ ms and increase from baseline $\geq 100$ ms	
QRS	>110 ms >160 ms Increase from baseline $\geq 20$ ms Increase from baseline $\geq 40$ ms	
QTc Borderline Prolonged* Additional	>450 ms and <500ms (Male); >470 ms and <500ms (Female) $\geq 500$ ms  Increase from baseline Increase from baseline >10 ms Increase from baseline >20 ms Increase from baseline >40 ms Increase from baseline >60 ms	To be applied to any kind of QT correction formula.

Note: Based on CPMP 1997 guideline.

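### Level-only ECG and pulse-rate threshold rows (mainly QTc and QRS) count subjects who already met the cut at baseline, and nothing planned separates them from new abnormalities

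*SAP*

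**What the plan says.** SAP 8.4.3 (ECG) plans: "The number and percentage of subjects meeting at least 1 threshold analysis criterion during the TE period of the corresponding part will be summarized". SAP 8.4.4 (vital signs) plans: "The number and percentage of subjects meeting at least 1 threshold analysis criterion during the TE period for the corresponding part will be summarized". Protocol 12.3.3.3 has the same rule: "The number and percentage of subjects with at least 1 threshold analysis event during the TE Period in this study will be summarized". None of these texts sets aside subjects who met the criterion at baseline, and none plans a categorical shift.

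Two neighbouring sections do bring in baseline status. For laboratory tests, SAP 8.4.2 adds: "The threshold analysis criterion shift from baseline will also be summarized for selected laboratory test values". For oximetry, SAP 8.4.5 plans "The number and percentage of subjects with shift changes from baseline (normal/missing and low according to the reference range") to the lowest on-treatment saturation.

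The criteria are in SAP Appendix D. In Table 11-5 the borderline QTc row reads ">450 ms and <500ms (Male); >470 ms and <500ms (Female"). A QTc row at >=500 ms and separate rows for increases of >10, >20, >40 and >60 ms follow. QRS has level rows (>110, >160 ms) and separate change rows (>=20, >=40 ms). Table 11-6 applies the heart-rate criteria to pulse rate.

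**The concern.** ECGs and vital signs are named in the primary endpoint, and the study has one arm and a descriptive analysis. No control group shows how common a QTc above 450 ms or a QRS above 110 ms would be without the switch of treatment. A level-only row therefore mixes subjects who arrived with the abnormality and subjects who developed it on ELX/TEZ/IVA.

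The separate change rows do not resolve this. They are counts of their own, so the table does not show whether the subjects above the level are the ones whose value rose. Someone using the level rows to judge cardiac safety could read too much into them. Equally, a few new cases could be hidden among many stable ones.

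**Working it through.** **The plan's only precision figure.** SAP 6.2 states that with over 400 subjects and no events in a Preferred Term, a frequency above 1% is ruled out with 95% confidence. At n = 400 the one-sided upper bound is 1 - 0.05^(1/400) = 0.746%, and the two-sided Clopper-Pearson bound is 1 - 0.025^(1/400) = 0.918%. The figure reproduces, but it concerns adverse-event terms and does not bear on threshold rows.

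**Which rows are exposed.** Each Appendix D parameter was checked for a row joining level and change at the same cut.

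| Parameter | Level cuts | Joint level-plus-change row |
|---|---|---|
| QTc | >450/>470 to <500; >=500 ms | none |
| QRS | >110; >160 ms | none |
| PR | >=240; >=300 ms | only at >=200 ms |
| Heart and pulse rate | <50; >100 bpm | yes |
| Heart and pulse rate | <45; >115; >130 bpm | none at these cuts |
| SBP | >140; >160; <90; <80 mmHg | yes, every cut |
| DBP | >90; >100; <60; <45 mmHg | yes, every cut |
| Weight | none (percent change only) | not needed |

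QTc and QRS have no joint row at any level. PR and the extreme rate cuts are partly served, because the joint row at a milder level excludes a stable value.

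**How easily a baseline case is counted.** One qualifying TE Period value is enough. Part A schedules six post-baseline ECGs up to Week 96 (Day 15; Weeks 8, 24, 48, 72 and 96). The ECG rule in SAP Appendix A uses every same-day reading for threshold purposes.

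**Size, by illustration.** Let b be the share meeting the cut at baseline, r the share of those who meet it again in the TE Period, and i the new-onset risk in the rest. All three are assumptions; the documents give none of them.

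- Reported proportion = b x r + (1 - b) x i
- Pre-existing share of those counted = b x r / [b x r + (1 - b) x i]

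For n = 400, cells show subjects reported (percent) and the pre-existing share:

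| b | r = 0.5, i = 5% | r = 0.5, i = 2% | r = 1, i = 5% | r = 1, i = 2% |
|---|---|---|---|---|
| 1% | 21.8 (5.5%); 9% | 9.9 (2.5%); 20% | 23.8 (6.0%); 17% | 11.9 (3.0%); 34% |
| 5% | 29.0 (7.3%); 34% | 17.6 (4.4%); 57% | 39.0 (9.8%); 51% | 27.6 (6.9%); 72% |
| 10% | 38.0 (9.5%); 53% | 27.2 (6.8%); 74% | 58.0 (14.5%); 69% | 47.2 (11.8%); 85% |

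Lowest case: 0.005 / (0.005 + 0.0495) = 9%. Highest case: 0.100 / (0.100 + 0.018) = 85%. If nobody meets the cut at baseline, the share is zero, so a rare criterion may be unaffected.

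**The case against.** The other side has several sound points.

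- **Scope.** A reader might infer that all ECG and vital-sign threshold counts are affected. Appendix D does not support that. Every SBP and DBP cut has a joint row, weight uses change only, and heart rate and PR have some joint rows. This limits the point to the level-only rows.
- **Labelling.** A reader might infer that the SAP presents these subjects as new cases. It does not: it reports who met a criterion in the TE Period. The protocol speaks of a threshold event but does not call it new onset either. The risk lies in interpretation.
- **Other sources.** SAP 8.4.3 also promises that "a summary of observed values and change from baseline values (in msec) will be provided at each visit", together with individual listings, and clinically significant worsening is recorded as an adverse event (Protocol 13.1.1.2). These help, but visit means do not show who crossed a cut, and listings for over 400 subjects are not a summary.
- **Parity.** A reader might infer that laboratory tests and oximetry already have the split asked for here. They do not. The laboratory shift covers selected tests, the laboratory threshold count has no baseline exclusion, and oximetry pools normal with missing. Those sections show that the SAP uses baseline shifts elsewhere, but the denominator proposed below goes further.
- **Consistency.** The SAP follows the protocol, which plans no shift for ECGs or vital signs. Nothing is contradicted. The protocol does allow further ECG and vital-sign analyses in the SAP.

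**Conclusion.** The point holds for the level-only rows: QTc and QRS first, then PR >=240/>=300 ms and heart or pulse rate <45, >115 and >130 bpm. As planned, these rows cannot tell a stable pre-existing abnormality from a new one, and no other planned summary table does so at the same cut. It is a worthwhile, inexpensive improvement to a descriptive primary safety analysis, not an error that invalidates it.

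The size is unknown. Across the assumed ranges (prevalence 1-10%, persistence 0.5-1, onset 2-5%), pre-existing cases are about 9% to 85% of those counted. A reader might infer that they must be the large majority. Full persistence with 1% onset does give 67% at 2% prevalence (0.020/0.0298) and 92% at 10% (0.100/0.109), but the documents support neither assumption.

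**What to change.** In SAP 8.4.3, and for pulse rate in 8.4.4, keep the planned overall counts. For the level-only rows listed above, add:

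1. A shift from baseline category (met / not met / missing) to the worst TE Period value, taking the lowest value for the <45 bpm cut and the highest for the others.
2. The number and percentage of new occurrences, with subjects not meeting the criterion at baseline as the denominator. The borderline QTc band is capped at 500 ms, so treat QTc as ordered categories; a subject at >=500 ms at baseline who later falls into the band is then not called new.
3. A footnote on what new means. Baseline is the last value before ELX/TEZ/IVA in Part A (SAP 8.1), generally after VX-659/TEZ/IVA, so new means since the switch, not since an untreated state. Part B uses the same baseline, so new there means relative to the Part A baseline and includes abnormalities that first arose in Part A and persist.

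SBP, DBP and weight need no change. Day 1 ECGs and vital signs are already scheduled, so no data collection is added and no subject is dropped. The cost is SAP wording and a few extra table columns.
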